## SUMMARY OF CHANGES FROM PREVIOUS VERSION

An overview of the updates incorporated into Amendment 4 is provided in the table below.

Protocol Amendments		
Summary of Change(s) Since Last Version of Approved Protocol		
Amendment Number	Amendment Date	Global
4	31 May 2018	
Description of Change		Section(s) Affected by Change
Updated Inclusion Criterion 4 to state that subjects must meet at least 1 of the 2 criteria below: 
 
a. Have a positive AdenoPlus® test at Visit 1 in at least 1 eye.
 
b. Have at least 2 of the following 5 criteria, based upon medical history and examination:               
 
i. Symptoms within the past 7 days consistent with acute upper respiratory tract infection (eg, sore throat, cough, rhinorrhea, etc)
 
ii. Contact within the past 7 days with family members or other individuals with recent onset of symptoms consistent with conjunctivitis
 
iii. Acute onset within the past 4 days of 1 or more of the following ocular symptoms: burning/irritation, foreign body sensation, light sensitivity
 
iv. Enlarged periauricular lymph node(s)
 
v. Presence of follicles on tarsal conjunctiva
 
 
 
 
Note: If the subject only meets Inclusion Criterion 4a (a positive AdenoPlus test in at least 1 eye), then the same eye must meet Inclusion Criterion 5.
		Synopsis Section 4.1 Section 7.2.1.3
Updated the approximate number of sites.		Synopsis

## ABBREVIATIONS

AE	adverse event
BCVA	Best Corrected Visual Acuity
CC-IFA	cell culture-immunofluorescence assay
CRA	clinical research associate
CRF	case report form
CRO	contract research organization
eCRF	electronic case report form
EC	ethics committee
EU	European Union
FDA	Food and Drug Administration
GCP	Good Clinical Practice
HIPAA	Health Insurance Portability and Accountability Act
HSV	Herpes Simplex Virus
ICH	International Conference on Harmonisation
IOP	intraocular pressure
IRB	Institutional Review Board
IRT	interactive response technology
ITT	Intent to Treat
mITT	Modified Intent to Treat
MRSA	methicillin-resistant Staphylococcus aureus
PVP-I	povidone-iodine
qPCR	quantitative polymerase chain reaction
SAE	serious adverse event
SAP	statistical analysis plan
TEAE	treatment- emergent adverse event
US	United States

## STUDY SYNOPSIS

Protocol number: SHP640-302	Drug: SHP640
Title of the study: A Phase 3, Multi-center, Randomized, Double-Masked Study to Evaluate the Clinical Efficacy and Safety of SHP640 (PVP-Iodine 0.6% and Dexamethasone 0.1%) Ophthalmic Suspension Compared to Placebo in the Treatment of Adenoviral Conjunctivitis	
Number of subjects (total and for each treatment arm):	
Total subjects: Approximately 284	
SHP640 treatment arm: Approximately 142	
Placebo treatment arm: Approximately 142	
Investigator(s): multicenter study	
Site(s) and Region(s):	
The study will be conducted in approximately 68 sites across North America, South America, Asia/Pacific, Europe, and Africa.	
Study period (planned): December 2016 to May 2018	Clinical phase: 3
Objectives:	
Primary:	
The primary objective of this study is to evaluate the efficacy of SHP640 based on clinical resolution (defined as absence of bulbar conjunctival injection and watery conjunctival discharge) compared with placebo in the treatment of subjects with adenoviral conjunctivitis in the study eye at Visit 3 (Day 6).	
Secondary:	
The key secondary objective of the study is to evaluate the efficacy of SHP640 based on adenoviral eradication (defined as negative cell culture-immunofluorescence assay [CC-IFA]) compared with placebo in the treatment of subjects with adenoviral conjunctivitis in the study eye at Visit 3 (Day 6).	
Secondary objectives of this study are as follows:	


• To evaluate the effect of treatment in the study eye, for the following endpoints:

○ Adenovirus viral titer assessed by quantitative polymerase chain reaction (qPCR) at Visit 3 (Day 6) and 4 (Day 8)

○ Adenoviral eradication as assessed by CC-IFA at Visits 2 (Day 3), 4 (Day 8) and 5 (Day 12)

○ Clinical resolution of adenoviral conjunctivitis at Visits 2 (Day 3), 4 (Day 8) and 5 (Day 12)

○ Individual clinical signs (bulbar conjunctival injection and watery conjunctival discharge) at Visits 2 (Day 3), 3 (Day 6), 4 (Day 8) and 5 (Day 12)

○ The Global clinical score (sum of bulbar conjunctival injection and watery conjunctival discharge) and change from baseline in the global clinical score at Visits 2 (Day 3), 3 (Day 6), 4 (Day 8) and 5 (Day 12)

○ Modified clinical resolution, defined as a global clinical score of 0 or 1, at Visits 2 (Day 3), 3 (Day 6), 4 (Day 8) and 5 (Day 12)

○ Expanded clinical resolution, defined as a global clinical score of 0, 1, or 2 with neither

	

injection nor discharge having a score of 2, at Visits 2 (Day 3), 3 (Day 6), 4 (Day 8) and 5 (Day 12)
○ Time to clinical resolution based upon assessments at Visits 2 (Day 3), 3 (Day 6), 4 (Day 8), and 5 (Day 12)
● To assess the status of cross-over infection (as assessed by CC-IFA) to a subject's fellow eye at Visits 2 (Day 3), 3 (Day 6), 4 (Day 8) and 5 (Day 12) for subjects with only 1 infected eye at baseline
● To evaluate the safety and tolerability of SHP640 compared to placebo in the treatment of subjects with adenoviral conjunctivitis.

**Rationale:**

The clinical presentation of conjunctivitis is often nonspecific and differential diagnosis of different types of conjunctivitis can be challenging. Diagnostic testing to differentiate the underlying cause of infection is rarely performed in a clinical setting; misdiagnosis can occur in up to 50% of cases, which often results in improper antibiotic treatment. Currently there is no approved medication for the treatment of adenoviral conjunctivitis. An unmet need therefore exists for a safe and efficacious treatment that addresses infectious conjunctivitis (adenoviral and bacterial).

By combining PVP-I, a potent topical antiseptic with proven antiviral and antibacterial activity, with dexamethasone, a topical steroid, SHP640 will enable the treatment of both the infectious and inflammatory components of adenoviral and bacterial conjunctivitis even when the cause of infection is unclear.

**Investigational product, dose, and mode of administration:**

The drug product is SHP640 (0.1% Dexamethasone and 0.6% PVP-I) Ophthalmic Suspension.

The placebo product is Placebo Ophthalmic Solution.

Subjects will instill 1 drop of investigational product in each eye 4 times daily (with a minimum of 2 hours between doses) for 7 days.

**Methodology:**

Once screening and baseline assessments are complete and subjects are confirmed eligible to enroll in the study, subjects will be randomized, and investigational product will be administered on the same day (Day 1). The first dose will be administered by site staff on Day 1, and thereafter subjects will administer 1 drop in each eye 4 times a day (QID) for 7 days. Additional visits will occur on Visit 2 (Day 3), Visit 3 (Day 6), Visit 4 (Day 8), and Visit 5 (Day 12). The study will last up to 13 days.

**Inclusion and exclusion criteria:****Inclusion Criteria:**

1. An understanding, ability, and willingness to fully comply with study procedures and restrictions (by the parent(s), guardian, or legally authorized representative, if applicable).
2. Ability to voluntarily provide written, signed, and dated (personally or via a parent(s), guardian, or legally authorized representative(s) informed consent (and assent, if applicable) to participate in the study.
3. Subjects of any age at Visit 1 (Note: subjects < 3 months of age at Visit 1 must have been full-term, ie  $\geq 37$  weeks gestational age at birth).
4. Meet at least 1 of the 2 criteria below:
  - a. Have a positive AdenoPlus® test at Visit 1 in at least 1 eye.
  - b. Have at least 2 of the following 5 criteria, based upon medical history and examination:
    - vi. Symptoms within the past 7 days consistent with acute upper respiratory tract infection (eg, sore throat, cough, rhinorrhea, etc)

- vii. Contact within the past 7 days with family members or other individuals with recent onset of symptoms consistent with conjunctivitis
- viii. Acute onset within the past 4 days of one or more of the following ocular symptoms: burning/irritation, foreign body sensation, light sensitivity
- ix. Enlarged periauricular lymph node(s)
- x. Presence of follicles on tarsal conjunctiva

Note: If the subject only meets Inclusion Criterion 4a (a positive AdenoPlus test in at least 1 eye), then the same eye must meet Inclusion Criterion 5.

- 5. Have a clinical diagnosis of suspected adenoviral conjunctivitis in at least 1 eye confirmed by the presence of the following minimal clinical signs and symptoms in that same eye:
  - Report presence of signs and/or symptoms of adenoviral conjunctivitis for  $\leq$  4 days prior to Visit 1
  - Bulbar conjunctival injection: a grade of  $\geq 1$  (mild) on a 0-4 Bulbar Conjunctival Injection Scale.
  - Watery conjunctival discharge: a grade of  $\geq 1$  (mild) on a 0-3 Watery Conjunctival Discharge Scale
- 6. Be willing to discontinue contact lens wear for the duration of the study.
- 7. Have a Best Corrected Visual Acuity (BCVA) of 0.60 logMAR or better in each eye as measured using an Early Treatment Diabetic Retinopathy Study (ETDRS) chart. BCVA will be assessed by an age appropriate method in accordance with the AAP Policy Statement for Visual System Assessment in Infants, Children, and Young Adults by Pediatricians (Donahue and Baker 2016; American Academy of Pediatrics 2016). The policy statement recommends formal vision screening can begin at 3 years of age. VA measurements for children under the age of 3 will be done at the discretion of the investigator. If not done, child should be able to fixate on and follow a moving object, except subjects  $<2$  months of age who have not yet developed this ability. Subjects  $<2$  months will be enrolled at the discretion of the investigator.
- 8. Male, or non-pregnant, non-lactating female who agrees to comply with any applicable contraceptive requirements of the protocol or females of non-childbearing potential.

**Exclusion Criteria:**

Subjects are excluded from the study if any of the following exclusion criteria are met:

- 1. Current or recurrent disease that could affect the action, absorption, or disposition of the investigational product, or clinical or laboratory assessments, per investigator's discretion.
- 2. Current or relevant history of physical or psychiatric illness, any medical disorder that may make the subject unlikely to fully complete the study, or any condition that presents undue risk from the investigational product or procedures.
- 3. Have known or suspected intolerance or hypersensitivity to the investigational product, closely related compounds, or any of the stated ingredients.
- 4. Prior enrollment in a FST-100 or SHP640 clinical study.
- 5. Subjects who are employees, or immediate family members of employees (who are directly related to study conduct), at the investigational site.
- 6. Have a history of ocular surgical intervention within  $\leq$  6 months prior to Visit 1 or planned for the period of the study.
- 7. Have a preplanned overnight hospitalization during the period of the study.
- 8. Have presence of any intraocular, corneal, or conjunctival ocular inflammation (e.g., uveitis, iritis, ulcerative keratitis, chronic blepharoconjunctivitis), other than adenoviral conjunctivitis.
- 9. Have presence of corneal subepithelial infiltrates at Visit 1.

10. Have active or history of ocular herpes.
11. Have at enrollment or within  $\leq$ 30 days of Visit 1, a clinical presentation more consistent with the diagnosis of non-infectious conjunctivitis (except presumed seasonal/perennial allergic conjunctivitis) or non-adenoviral ocular infection (e.g., bacterial, fungal, acanthamoebal, or other parasitic). Note: history or concomitant presence of presumed seasonal or perennial allergic conjunctivitis signs/symptoms is not exclusionary.
12. Neonates or infants (ie, subjects less than 12 months of age) who have suspected or confirmed (based on the result of any test conducted prior to screening) conjunctivitis of gonococcal, chlamydial, herpetic or chemical origin.
13. Neonates or infants (ie, subjects less than 12 months of age) whose birth mothers had any sexually transmitted disease within 1 month of delivery or any history of genital herpes.
14. Presence of nasolacrimal duct obstruction at Visit 1 (Day 1).
15. Presence of any significant ophthalmic condition (eg, retinopathy of prematurity, congenital cataract, congenital glaucoma) or other congenital disorder with ophthalmic involvement that could affect study variables.
16. Be a known intraocular pressure (IOP) steroid responder, have a known history or current diagnosis of glaucoma, or be a glaucoma suspect.
17. Have any known clinically significant optic nerve defects.
18. Have a history of recurrent corneal erosion syndrome, either idiopathic or secondary to previous corneal trauma or dry eye syndrome; presence of corneal epithelial defect or any significant corneal opacity at Visit 1.
19. Presence of significant, active condition in the posterior segment which requires invasive treatment (eg, intravitreal treatment with VEGF inhibitors or corticosteroids) and may progress during the study participation period.
20. Have used any topical ocular or systemic anti-virals or antibiotics within  $\leq$  7 days of enrollment.
21. Have used any topical ocular NSAIDs within  $\leq$  1 day of enrollment.
22. Have used any topical ophthalmic steroids in the last  $\leq$ 14 days.
23. Have used any systemic corticosteroid agents within  $\leq$  14 days of Day 1. Stable (initiated  $\geq$  30 days prior to enrollment) use of inhaled and nasal corticosteroids is allowed, given no anticipated change in dose for the duration of the study. Topical dermal steroids are allowed except in the peri-ocular area.
24. Have used non-corticosteroid immunosuppressive agents within  $\leq$  14 days of Day 1.
25. Have used any topical ophthalmic products, including tear substitutes, and over-the-counter preparations such as lid scrubs, within 2 hours of Visit 1 and be unable to discontinue all topical ophthalmic products for the duration of the study. Use of hot or cold compresses is also not permitted during the study.
26. Have any significant ocular disease (eg, Sjogren's syndrome) or any uncontrolled systemic disease or debilitating disease (e.g., cardiovascular disease, hypertension, sexually transmitted diseases/infections, diabetes or cystic fibrosis), that may affect the study parameters, per investigator's discretion.
27. Any known history of immunodeficiency disorder or known active conditions predisposing to immunodeficiency, such as human immunodeficiency virus, hepatitis B or C, evidence of active hepatitis A (antihepatitis A virus immunoglobulin M), or organ or bone marrow transplantation.
28. Within 30 days prior to the first dose of investigational product:
  - Have used an investigational product or device, or
  - Have been enrolled in a clinical study (including vaccine studies) that, in the investigator's

opinion, may impact this Shire-sponsored study.

**Maximum duration of subject involvement in the study:**

Subject participation will last up to 13 days.

Screening, randomization and the first treatment administration will occur at Visit 1 (Day 1).

Additional visits will occur on Visit 2 (Day 3), Visit 3 (Day 6), Visit 4 (Day 8), and Visit 5 (Day 12).

All follow-up procedures will be conducted at Visit 5 (Day 12).

**Endpoints and statistical analysis:**

*Primary Efficacy Endpoint:*

Clinical resolution status (defined as absence of bulbar conjunctival injection and watery conjunctival discharge) in the study eye at Visit 3 (Day 6) between SHP640 and placebo.

*Key Secondary Efficacy Endpoints:*

Adenoviral eradication status (defined as negative cell culture-immunofluorescence assay [CC-IFA]) in the study eye at Visit 3 (Day 6).

*Secondary Efficacy Endpoints:*

- Absolute and change from baseline in adenovirus viral titer as assessed by qPCR at Visit 3 (Day 6) and 4 (Day 8) in the study eye
- Adenoviral eradication status as assessed by CC-IFA at Visits 2 (Day 3), 4 (Day 8) and 5 (Day 12) in the study eye
- The clinical resolution status of adenoviral conjunctivitis at Visits 2 (Day 3), 4 (Day 8) and 5 (Day 12) in the study eye
- The individual clinical signs score (bulbar conjunctival injection and watery conjunctival discharge) and change from baseline at Visits 2 (Day 3), 3 (Day 6), 4 (Day 8) and 5 (Day 12) in the study eye
- The global clinical score (as defined as the sum of bulbar conjunctival injection and watery conjunctival discharge) and change from baseline in the global clinical score at Visits 2 (Day 3), 3 (Day 6), 4 (Day 8) and 5 (Day 12) in the study eye
- Modified clinical resolution status, defined as a global clinical score of 0 or 1, at Visits 2 (Day 3), 3 (Day 6), 4 (Day 8) and 5 (Day 12) in the study eye
- Expanded clinical resolution status, defined as a global clinical score of 0, 1, or 2 with neither injection nor discharge having a score of 2, at Visits 2 (Day 3), 3 (Day 6), 4 (Day 8) and 5 (Day 12) in the study eye
- The status of cross-over infection (as assessed by CC-IFA) to a subject's fellow eye at Visits 2 (Day 3), 3 (Day 6), 4 (Day 8) and 5 (Day 12) for subjects with only 1 infected eye at baseline
- Time to clinical resolution based upon assessments at Visits 2 (Day 3), 3 (Day 6), 4 (Day 8), and 5 (Day 12) in the study eye

*Safety Endpoints:*

- Best Corrected Visual Acuity (BCVA)
- Slit Lamp Biomicroscopy
- Intraocular Pressure
- Non-dilated/ Dilated Fundus Examination
- Urine Pregnancy Testing (for females of childbearing potential)

- Adverse Events (AEs)

*Statistical Methods:*

The analyses on primary, key secondary, secondary, and exploratory efficacy endpoints will be performed on the mITT population (unless specified otherwise) and will be presented by treatment group. Additional sensitivity analyses may be conducted on the ITT population. Safety analysis will be conducted on the safety population.

For both efficacy and safety analyses, baseline is defined as the assessments taken at Visit 1 (Day 1).

*Analyses Populations:*

The **Safety Population** will include all subjects who receive at least one dose of investigational product

The **Intent to Treat (ITT) Population** will include all randomized subjects.

The **Modified Intent to Treat (mITT)** population consists of a subset of the ITT population who receives at least one dose of investigational product and have a positive CC-IFA adenovirus test at baseline in the study eye.

*Designation of Study Eye:*

The study eye for analyses will be defined as follows, where an eligible eye is an eye with a score of at least 1 for both watery conjunctival discharge and bulbar conjunctival redness at baseline (baseline is defined as the assessments taken at Visit 1 (Day 1)):

- For subjects with both eyes eligible and both with a positive CC-IFA result at baseline or both eyes eligible and both with a negative CC-IFA result at baseline, the study eye will be the eye with the highest global clinical score (sum of the scores for discharge and redness) at baseline. If both eyes have the same global clinical score at baseline, then the study eye will be the right eye.
- For subjects with both eyes eligible with a positive CC-IFA result in one eye at baseline, the baseline CC-IFA positive eye will be the study eye.
- For subjects with only one eligible eye, the eligible eye will be the study eye irrespective of its baseline CC-IFA status.

*Primary Efficacy Analyses:*

The primary efficacy endpoint of clinical resolution will be analyzed based on the mITT population at Visit 3 (Day 6). If subjects drop out of the study before Visit 3, then the last observation will be carried forward (LOCF) for the determination of clinical resolution of the eye.

The null hypothesis to be tested is that there is no difference in proportion of subjects with clinical resolution in the study eye between SHP640 Ophthalmic Solution and Placebo with the alternative of the non-zero difference in the proportion with clinical resolution between them.

The proportion of subjects with clinical resolution will be compared with two-sided Fisher's Exact test at 5% level of significance.

Sensitivity analyses will be done on the primary efficacy endpoint using additional statistical method(s) including other methods of imputation of missing data.

*Key Secondary Efficacy Analyses:*

In order to maintain the study-wide Type I error at 5.0%, the primary and key secondary hypotheses will be tested sequentially using two-sided Fisher's exact test.

The hypothesis test for the key secondary efficacy endpoint will not be performed unless hypothesis test for the primary efficacy endpoint is significant.

Sensitivity analyses will also be done on key secondary efficacy endpoints using similar methods as described above.

*Secondary Efficacy Analyses:*

All secondary efficacy analyses will be performed on the mITT and presented by treatment group. No hypothesis testing is planned for the secondary efficacy endpoints. All secondary efficacy endpoints will be summarized by treatment groups using descriptive statistics at each assessment visit. Continuous endpoints will be summarized by number of subjects (n), mean, median, standard deviation, minimum, maximum and confidence intervals. Binary endpoints will be summarized by number of subjects (n), frequencies proportions and confidence intervals. Time to event endpoint will be summarized by Kaplan-Meier survival estimates.

*Safety Analyses:*

Safety data will be presented for the Safety Population by treatment group and overall. Adverse events will be coded using the Medical Dictionary for Regulatory Activities. The number of subjects and percentage with a treatment-emergent adverse event (TEAE) as well as the number of TEAEs will be calculated overall, by SOC, by preferred term, and by treatment group and overall. Treatment-emergent adverse events will be further summarized by severity and relationship to investigational product. Adverse events related to investigational product, AEs leading to withdrawal, SAEs, and deaths will be similarly summarized and listed. Any AE that occurs after the first dose of investigational product instillation will be considered a TEAE.

Generally, TEAEs will be presented separated by whether or not the AE was an ocular or non-ocular AE.

BCVA, Slit Lamp Biomicroscopy, intraocular pressure, non-dilated/dilated fundus exam, and urine pregnancy test (for females of childbearing potential), will be descriptively summarized by treatment group and overall at each applicable visit.

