##### 4.1 Inclusion Criteria

The subject will not be considered eligible for the study without meeting all of the criteria below.

1. An understanding, ability, and willingness to fully comply with study procedures and restrictions (by the parent(s), guardian, or legally authorized representative, if applicable).
2. Ability to voluntarily provide written, signed, and dated (personally or via a parent(s), guardian, or legally-authorized representative(s) informed consent (and assent, if applicable) to participate in the study.
3. Subjects of any age at Visit 1 (Note: subjects < 3 months of age at Visit 1 must have been full-term, ie  $\geq 37$  weeks gestational age at birth).
4. Meet at least 1 of the 2 criteria below:
  - a. Have a positive AdenoPlus® test at Visit 1 in at least 1 eye.
  - b. Have at least 2 of the following 5 criteria, based upon medical history and examination:
    - i. Symptoms within the past 7 days consistent with acute upper respiratory tract infection (eg, sore throat, cough, rhinorrhea, etc)
    - ii. Contact within the past 7 days with family members or other individuals with recent onset of symptoms consistent with conjunctivitis
    - iii. Acute onset within the past 4 days of 1 or more of the following ocular symptoms: burning/irritation, foreign body sensation, light sensitivity
    - iv. Enlarged periauricular lymph node(s)
    - v. Presence of follicles on tarsal conjunctiva

Note: If the subject only meets Inclusion Criterion 4a (a positive AdenoPlus test in at least 1 eye), then the same eye must meet Inclusion Criterion 5.

5. Have a clinical diagnosis of suspected adenoviral conjunctivitis in at least 1 eye confirmed by the presence of the following minimal clinical signs and symptoms in that same eye:
  - Report presence of signs and/or symptoms of adenoviral conjunctivitis for  $\leq 4$  days prior to Visit 1
  - Bulbar conjunctival injection: a grade of  $\geq 1$  on 0-4 scale of Bulbar Conjunctival Injection Scale
  - Watery conjunctival discharge: a grade of  $\geq 1$  (mild) on a 0-3 Watery Conjunctival

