#### **7.2.3.8      Health-related Quality of Life Assessments**

Ocular discomfort associated with conjunctivitis symptoms will be assessed through the Ocular Discomfort Scale. The Ocular Discomfort Scale is composed of three items: pain, itching, and foreign body sensation. All items will be evaluated using a 0-10 scale. A separate scale will be administered for children less than 8 years of age (binary ocular discomfort). Please see the Study Operations Manual for a detailed description of this assessment.

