5. SUBJECT DISPOSITION

A listing of all Screen Failures (ie, subjects who were screened but not randomized) will be presented along with reasons for screen fail.

The number of subjects included in each subject population (ie, Screened, Safety, ITT and mITT) will be summarized by randomized treatment group, age strata and overall except for the Screened Set, which will be summarized for all subjects only.

The number and percentage of subjects who completed and prematurely discontinued during the Double-masked Evaluation Phase will be presented for each treatment group, age strata and overall. Reasons for premature discontinuation from the Double-masked Evaluation Phase as recorded on the termination page of the eCRF will be summarized (number and percentage) by treatment group, age strata and overall. All percentages will be based on the number of subjects in the ITT Population.

A listing of disposition will be provided for all subjects. All subjects who prematurely discontinued during the Double-masked Evaluation Phase will be listed by discontinuation reason.

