11.1 Adverse Events

AEs will be coded using MedDRA version 19.1. Any AE that occurs after the first dose of investigational product instillation will be considered a treatment- emergent adverse event (TEAE).

An overall summary of the number of subjects with TEAEs will be presented, including the number and percentage of subjects with any TEAEs, ocular TEAEs, non-ocular TEAEs, TEAEs leading to death, serious TEAEs, TEAEs related to investigational product and TEAEs leading to discontinuation of investigational product as well as the total number of events in each category.

The number and percentage of subjects reporting TEAEs in each treatment group and across all subjects will be tabulated by System Organ Class (SOC) and Preferred Term (PT) as well as by SOC, PT, and maximum severity. TEAEs considered related to investigational product will also be summarized by SOC and PT. If more than 1 AE occurs with the same SOC/PT for the same subject, then the subject will be counted only once for that SOC/PT using the most severe and most related occurrence for the summarization by severity and by relationship to investigational product, respectively. The incidence of common TEAEs ($\geq 5\%$ of subjects in any treatment group) will also be summarized by SOC and PT. Serious TEAEs, TEAEs leading to discontinuation of investigational product and TEAEs leading to death, will be summarized by SOC, PT and treatment group and across all subjects. The number and percentage of subjects reporting local tolerability TEAEs (overall, related to IP and not related to IP) in each treatment group and across all subjects will also be tabulated by SOC and PT. PTs that are considered to be local tolerability AEs will be provided by global drug safety (GDS) before database lock. Separate tables will be generated for ocular TEAEs and non-ocular TEAEs. For all above tables, ocular TEAEs will be summarized at subject level and also by study eye, fellow eye and both eyes.

Listings of all TEAEs will be provided by subject.

Pre-treatment events (captured on the AE form that occurred prior to the first dose of investigational product) will be listed by subject but not tabulated.

Imputed dates, severity and relationship (see Section 18.7, 18.8 and 18.9 respectively for imputation rules) to investigational product will be marked in the listings.

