17. CHANGES TO ANALYSES SPECIFIED IN PROTOCOL

Since a decision has been made to early terminate the trial, an abbreviated Clinical Study Report (CSR) will be generated, which will contain a full report of information related to safety and abbreviated summary of efficacy evaluation. The majority of the efficacy analyses outlined in section 9.8, efficacy analysis section of the protocol will not be conducted. No hypothesis testing will be performed on any of the efficacy endpoint. Only descriptive statistics will be generated for clinical resolution status and adenoviral eradication status as outlined in section 10.2 of this SAP.

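### Every planned adverse-event table pools all ages from birth to adulthood, so no planned summary compares the arms within young children

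*Protocol*

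**What the plan says.** Protocol 4.1 admits "Subjects of any age at Visit 1", with only a full-term condition for the youngest infants. Randomisation is 1:1 within three strata: under 6, 6 to under 18, and 18 years or older (Protocol 3.1 and 6.2.2; SAP 2.2).

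For safety, the protocol synopsis and Protocol 9.9 both state: "Safety data will be presented for the Safety Population by treatment group and overall". SAP 11.1 begins its tabulation rule with "The number and percentage of subjects reporting TEAEs in each treatment group and across all subjects will be tabulated by System Organ Class (SOC"), and goes on to preferred term, severity, relationship, seriousness, discontinuation and local tolerability. Ocular events are also split by study eye, fellow eye and both eyes. Nothing is split by age. A further table covers preferred terms that reach 5% in either arm, all ages together.

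The age strata are used elsewhere. SAP 5 says that completion and discontinuation "will be presented for each treatment group, age strata and overall", giving Table 14.1.1.2. Protocol 9.8.2 and 9.8.3 planned paediatric summaries of the primary and key secondary efficacy endpoints, but there is no counterpart for adverse events. After early termination, SAP 17 calls for an abbreviated study report "which will contain a full report of information related to safety", while most efficacy analyses are dropped.

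**The concern.** Safety is the part of this trial that will be reported in full, and the population runs from newborns to adults. If SHP640 caused an ocular or local reaction mainly in young children, the planned tables would show one rate per arm averaged over all ages. The comparison of SHP640 with placebo among under-6s would appear in no table. Such a reaction could also fall below 5% of the pooled arm and so be absent from the common-event table.

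**Working it through.** **Table list.** In SAP section 21, none of Tables 14.3.1.1 to 14.3.4.1.3 names age. The safety outputs that are age-specific are not adverse-event outputs: the red reflex table and listing (14.3.6.4, 16.2.8.4) and the chlamydia/gonorrhoea listing for infants under 2 months (16.2.8.8). Protocol 9.10 and SAP 13 plan no other analysis.

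**What remains recoverable.** Stratum denominators are planned: population counts by arm and age stratum (SAP 5) and age strata within Safety Population demographics (SAP 7, Table 14.1.2.1.1). Numerators can be found by linking the TEAE listing (16.2.7.3) to the demographics listing (16.2.4.1). The age-specific comparison can therefore be derived, but it is not presented.

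**Size of the dilution.** The plan gives no figure on this point. Its sample-size statement does reproduce (exact Fisher power 90.1% at 92 per arm for 31% against 11%) but has no bearing here.

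Inputs: planned arm size 284/2 = 142 (protocol synopsis); threshold 5% of an arm (SAP 11.1). The share *s* of subjects under 6 is not in the documents and is varied. The reaction is assumed to occur only in that stratum.

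- Minimum count for the 5% table: 0.05 × 142 = 7.1, so 8 subjects; 7/142 = 4.9% stays out.
- Stratum rate needed for a pooled 5%: 5%/*s*.
- Chance of missing the table: P(X ≤ 7), with X binomial on the stratum size at the true stratum rate.

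| Share under 6 | About n per arm | Rate needed | Miss, true rate 20% | Miss, true rate 30% |
|---|---|---|---|---|
| 10% | 14 | 50% | about 100% | 97% |
| 15% | 21 | 33% | 96% | 72% |
| 20% | 28 | 25% | 82% | 36% |
| 30% | 43 | 17% | 35% | 3% |
| one third | 47 | 15% | 25% | 1% |

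For example, 7 affected among 28 young children is 25% of the stratum and 4.9% of the arm.

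The trial stopped early and the number randomised is not given. At an assumed 50 per arm, 3 subjects are needed. The chance of a miss at a true rate of 20% is then 80%, 68% and 40% for shares of 15%, 20% and 30%.

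**Precision of a stratum rate.** With assumed counts, 4 of 15 under-6s is 26.7% (exact 95% CI 7.8 to 55.1), and the same 4 in an arm of 100 is 4.0% (1.1 to 9.9).

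**The case against.** The strongest reply is that nothing here is inconsistent. Protocol and SAP agree on safety by arm and overall, age-specific summaries were planned only for efficacy, and the strata were introduced to keep the allocation ratio. Because allocation is 1:1 within strata, pooling does not by itself bias the comparison of arms. All of this stands, and it is why the point is an improvement only.

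A reader might infer three stronger things that the documents do not support.

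- **That a reaction in children would disappear from the report.** It would not. The common-event table is an additional digest. The ocular and non-ocular SOC/PT tables and the local-tolerability tables carry no cut-off, and every TEAE is listed by subject.
- **That the 5% rule should be applied within strata.** In a cell of 20 or fewer, a single case is already at least 5% (1/20), so the digest would drift towards the full table that is planned anyway.
- **That adverse events are ascertained differently in young children.** The protocol does say "A separate scale will be administered for children less than 8 years of age (binary ocular discomfort"), but that scale is a quality-of-life measure (Protocol 7.2.3.8), not how adverse events are elicited. Protocol 7.2.3.5 uses a general question at each visit and also lets the investigator identify events on examination.

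**Conclusion.** The point holds as a gap in presentation. No planned table compares TEAEs between arms within an age group, in a trial that enrols from birth and already summarises disposition by age stratum. This follows from the text and needs no assumption.

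The effect on the 5% table does rest on assumptions: the share under 6, the arm size, a reaction confined to that stratum, and independent subjects, although household members share an arm. Across the shares shown at 142 per arm and a true stratum rate of 30%, the chance of a miss runs from 97% down to 1%, and nothing in the documents says where this trial lies.

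One limit of source: the SAP implements protocol amendment 5, whereas the protocol available is amendment 4, and table specifications are in a separate document. The SAP's own table list still contains no adverse-event table by age.

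**What to change.** In SAP 11.1 and section 21, add repeats of Tables 14.3.1.1 (overall TEAEs), 14.3.1.2.1 (ocular TEAEs by SOC and PT) and 14.3.4.1.1 (ocular local tolerability) by treatment arm within the three randomisation age strata. Show counts, denominators and percentages, with no frequency cut-off and no tests. Leave the 5% rule as it is.

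The cost is three extra tables using an age grouping already needed for disposition; no new data are required. The drawback is imprecise percentages in small strata, more so after early termination. Showing the denominators makes that visible.
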